An analgesic alternative with few associated limitations is **pulsed electromagnetic field (PEMF)** therapy, also called pulsed short-wave therapy, pulsed radiofrequency energy therapy, and radiofrequency nonthermal diathermy.¹ Over the last 7 decades, PEMF has been used to treat acute and chronic pain, decrease inflammation and edema, and hasten wound healing and bone regeneration.¹ Possible mechanisms for the multiple clinical effects of PEMF are multifactorial, complex, and only partially understood.¹ The primary theory involves the promotion of calcium binding to calmodulin which activates endothelial and neuronal nitric oxide synthase isoforms, producing nitric oxide which has anti-inflammatory and analgesic effects, among other consequences

[figure not shown]
such as decreasing edema while increasing blood and lymph flow.¹

[figure not shown]
In 1947, the United States Federal Communications Commission assigned three frequencies for radiofrequency use in medical treatments: 40.68, 13.56 and 27.12 MHz.¹ Within just a few years, the first pulsed electromagnetic field generator was cleared by the United States Food and Drug Administration for use with patients using 27.12 MHz: the Diapulse.^{2,3}. Until relatively recently, available devices consisted of a large signal generator and bulky coil applicator that were not portable and produced significant electromagnetic interference, making them impractical for common use (Figure, right). However, over the past 70 years they have exhibited an extraordinary safety profile: these are noninvasive, nonpharmacologic devices, with no side effects, adverse events, or medication interactions; and the only

contraindications are pregnancy and an implanted pulse generator such as a cardiac pacemaker. Unlike opioids, there is no risk of abuse, dependence, and/or diversion.

More recently, small, simple, lightweight, battery-powered, noninvasive PEMF devices have received FDA clearance for use treating acute and chronic pain, including the ActiPatch and RecoveryRx for amputees and the initial 150 surgical subjects of Phase I (Model 088, BioElectronics, Frederick, Maryland; **Figure, below left**); as well as SofPulse for the subsequent 80 surgical subjects of Phase II (Endonovo Therapeutics, Woodland Hills, California; **Figure below right**). We will be using the devices for FDA-approved indications; in other words, on-label use.

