9. RESEARCH DESIGN AND METHODS

This will be a single-center (UCSD), randomized, participant- and observer-masked, sham-controlled, parallel-arm human subjects pilot study.

Enrollment. Participants will be consenting adults either (1) undergoing various surgical procedures usually resulting in moderate-to-severe postoperative pain, or (2) experience post-amputation phantom and/or residual limb pain. Study inclusion will be proposed (1) to eligible presurgical patients or (2) after an amputee contacts the investigators. If an individual desires study participation, written, informed consent will be obtained using a current UCSD IRB-approved ICF. The study population of interest includes adult women and men of all races, ethnicity, sexual identity, and socioeconomic status. Inclusion and exclusion criteria are listed in section #10 below.

Procedures. Following written, informed consent, we will record baseline anthropometric information (age, sex, height, weight, amputation details and current pain levels). Surgical participants will receive any standard peripheral nerve block(s) administered using bupivacaine or ropivacaine 0.5% with epinephrine (standard at UCSD) prior to undergoing their surgical procedure *per standard of care*.

Treatment Group Assignment. Each participant will be randomized to one of two treatment groups: *Active* or *Sham* treatment. For the initial 150 subjects of Phase I, there are sham RecoveryRx devices produced that are identical to active RecoveryRx devices, only they do not deliver PEMF. Randomization will be stratified by surgical procedure/amputation, in block sizes of 2. The computer-generated randomization lists will be created by the University of California San Diego Investigational Drug Service in a 1:1 treatment group ratio using opaque envelopes. For the initial 150 subjects of Phase I using RecoveryRx devices, the active and sham devices are indistinguishable in appearance, and therefore investigators, participants, and all clinical staff other than the individual who opens the randomization envelope and chooses a sham or active device will be masked to treatment group assignment for the duration of the data collection period. For the subsequent 80

subjects of Phase II, active SofPulse devices will be provided to patients randomized to the active treatment group; and sham RecoveryRx devices will be provided to the patients randomized to the sham treatment group.

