Clinical Trials (IMMPACT) consensus statement. All data collection will be through standard UCSD EPIC notes and patient interviews in-person during hospitalization or *via* a telephone call for outpatients. Postoperatively, surgical endpoints will be recorded such as surgical duration. All pain scores will be measured using the Numeric Rating Scale (0: no pain, 10: worst imaginable pain). On Days 35 and 70, amputees will be asked if they would want to continue using the device; and on Day 28 surgical patients will be asked if they would want to use the device if they were to have the same surgery in the future? For Phase II surgical participants, Days 21 and 28 will be excluded due to the shorter treatment period (8 days) of this device relative to that used in Phase I. At all time points for amputees, phantom and residual limb pain will be distinguished and recorded separately.

	Surgical Patients Postoperative Days								Amputees Post-Application Days						
Time Point:															
	1	2	3	7	14	21	28	180	0	2	4	7	21	28	35
Opioid consumption	•	•	•	•	•	•	•	•	•	•	•	•	•	•	•
Average Pain [NRS]	•	•	•	•	•	•	•	•	•	•	•	•	•	•	•
Worst Pain [NRS]	•	•	•	•	•	•	•	•	•	•	•	•	•	•	•
Brief Pain Inventory,				_	_	-	•							•	
Short Form				•	•	•	•		•					•	•
Patient Global												_	•	•	
Impression Change										•	•	•	•	•	•
Sleep disturbances	•	•	•		•	•	•		•	•	•			•	
(#) previous night	•				-					-	-				-
Passive flexion					•										
(knees and hips)															

Summary of post-enrollment assessments (color added for clarity)

Primary end points: This is an exploratory pilot study to assist in planning subsequent definitive trials and we therefore have no data analysis plan. For surgical patients, the two outcomes of primary interest will be (1) the "average" and "worst" pain measured with the Numeric Rating Scale (included in the Brief Pain Inventory pain domain), and (2) opioid consumption within the first 7 postoperative days. For amputees, the outcome measures of primary interest will be (1) the change in "average" residual and phantom limb pain scores between baseline and Day 28 of the initial treatment, as well as (2) the Patient Global Impression of Change on Day 28 of the initial treatment.

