For Phase II, there will be a total of 70 surgical participants, and these patients will be analyzed separately from Phase I surgical and amputation patients. Sample size calculations are based upon the hypothesis that pulsed electromagnetic field therapy decreases **pain** in the 7 days following moderate-to-severely painful surgical procedures. The primary outcome calculated as follows: for each participant all of the "average" and "worst" daily pain scores collected within the first 7 postoperative days will be summed. We will use these summed scores from participants having cholecystectomy (n=30), and hip and knee arthroplasty (n=40) to estimate a probable sample size.

We will consider a 33% reduction in pain scores to be the minimal clinically important difference [Farrar et al. J Pain Symptom Management 2003; 25: 406-11]. Based on values from patients receiving sham in Phase I, we anticipate the sham group to have an anticipated mean (SD) of 23.9 (12.3). Assuming a two-sided type I error protection of 0.05 and a power of 0.80, approximately 25 patients in each group are required (ClinCalc.com, accessed 2/23/23). To allow for a higher degree of variability than anticipated we will enroll a total of 70 participants in Phase II: cholecystectomy (n=30), and hip and knee arthroplasty (n=40).

Continuous, normally-distributed data will be reported as mean ± standard deviation. Nonparametric continuous or categorical data will be reported as median [10th-90th percentiles] or precents, as appropriate. Comparisons of independent samples will be performed using Student's t-test for parametric continuous variables or Mann-Whitney U test for nonparametric or categorical variables. The Chi Square test and Fisher's Exact test will be used for differences in proportions, as appropriate. P<0.05 will be considered statistically significant for the primary outcome. Results of comparisons in secondary outcomes will be interpreted as suggestive, requiring confirmation in a future trial before considering them as definitive.

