10. HUMAN PARTICIPANTS

We will recruit a convenience sample with a maximum of **270 participants in total (all participants who sign an informed consent included)**. Selection for inclusion will not be based on race, ethnicity, sexual identity, or socioeconomic status. There will be no participants from vulnerable populations, such as pregnant women, children, or prisoners.

Inclusion criteria (amputees): Adult patients of at least 18 years of age [19 years in Alabama and Nebraska], (1) with an upper or lower limb amputation at least 12 weeks prior to enrollment distal to the shoulder or hip (femoral head remaining), respectively, and including at least one metacarpal or metatarsal bone, respectively; (2) who experience at least moderate residual and/or phantom limb pain—defined as a 3 or higher on the Numeric Rating Scale (NRS; 0-10, 0= no pain; 10=worst imaginable pain)—at least daily for the previous 2 months; and (3) willing to avoid both changes to their analgesic regimen as well as elective surgical procedures for 70 days after initiation of treatment with PEMF therapy.

Inclusion criteria (surgical patients): Adult patients of at least 18 years of age undergoing one of the surgical procedures listed below:

- a. non-mastectomy breast surgery with a single-injection paravertebral nerve block
- b. laparoscopic or open cholecystectomy
- c. laparoscopic sleeve gastrectomy
- d. percutaneous nephrolithotomy
- e. ventral hernia repair
- f. inguinal hernia repair
- g. knee or hip arthroplasty
- h. foot/ankle surgery with at least moderate pain anticipated
- i. shoulder acromioclavicular joint repair, labral repair, subacromial decompression, or Bankart repair (without rotator cuff repair)
- j. hand/forearm/elbow/shoulder surgery with at least moderate pain anticipated
- k. spinal surgery with at least moderate pain anticipated

Exclusion criteria: (1) concurrent use of an implanted pulse generator (e.g., cardiac pacemaker); (2) pregnancy; (3) incarceration. **Surgical participants only:** (4) chronic opioid/tramadol use (daily use within the 2 weeks prior to surgery and duration of use > 4 weeks); (5) neuro-muscular deficit of the surgical area/limb; (6) a planned postoperative perineural local anesthetic infusion.

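### Phase II is randomised within surgical procedure, but no analysis by procedure is specified for its primary pain score; adding the strata costs no participants and can only help precision in the linear model, by an unknown amount.

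*Combined protocol and SAP*

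**What the plan says.** - **Randomisation (section 9, Treatment Group Assignment).** "Randomization will be stratified by surgical procedure/amputation, in block sizes of 2", allocated 1:1. Neighbouring sentences about devices distinguish the two phases; this one does not, and no other scheme is given for Phase II.
- **Phase II population (section 9, sample size paragraphs).** Two groups of operations are pooled ("cholecystectomy (n=30), and hip and knee arthroplasty (n=40"). The outcome is the sum of each participant's daily average and worst pain ratings over the first seven postoperative days.
- **Effect size (same place).** "We will consider a 33% reduction in pain scores to be the minimal clinically important difference". The expected sham mean (SD) is 23.9 (12.3), taken from Phase I and not split by procedure.
- **Tests (section 9, last paragraph).** Independent samples are compared by Student's "t-test for parametric continuous variables or Mann-Whitney U test for nonparametric or categorical variables". No stratified test, covariate or adjusted model appears anywhere.
- **Threshold (same paragraph).** "P<0.05 will be considered statistically significant for the primary outcome".
- **Status of the analysis (section 9, Primary end points).** The study is called exploratory: "we therefore have no data analysis plan".
- **Phase II size.** Section 9 gives 70 participants for Phase II in its sample size text. Section 7 has "SofPulse for the subsequent 80 surgical subjects of Phase II", and the Treatment Group Assignment text in section 9 also says 80.

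**The concern.** Blocks of 2 within procedure make the arms almost exactly balanced on procedure, so the difference in means is already free of procedure imbalance. An unadjusted t-test does not credit this: it estimates its standard error from the total spread, including any difference between cholecystectomy and arthroplasty. If the procedures differ in pain, that standard error is too large, the true type I error falls below 5%, and power and precision are lost. If they do not differ, nothing is lost.

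At stake is efficiency, not validity. It still counts here, because Aim 2 is to estimate the treatment effect, learn which procedures suit the technique and size later trials. An interval that carries between-procedure spread serves those purposes less well.

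A related, secondary point concerns amputees. Their pain outcome is the change from baseline to Day 28 of the initial treatment. Analysis of covariance on Day 0 pain uses the same data and in large samples is never less precise.

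**Working it through.** **1. Inputs.** From section 9: sham mean 23.9, SD 12.3, reduction 33%, two-sided alpha 0.05, power 0.80, strata of 30 and 40, 1:1 allocation (35 per arm). Target difference: 0.33 × 23.9 = 7.887 points. Assumed, because the documents are silent: a gap *D* between procedure means of 0, 5, 10 or 12 points.

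**2. The plan's own sample size.** n per arm = 2 × [SD × (1.960 + 0.842) / difference]² = 2 × [12.3 × 2.802 / 7.887]² ≈ 38.2, so 39 (40 with the noncentral t). The stated 25 per group is not reproduced; it would need a difference of about 9.75 points (41%) or an SD of about 9.95. That is a separate matter, but it means that 35 per arm gives an unadjusted power of about 75% (noncentral t), not 80%.

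**3. Share of variance due to procedure.** R² = (30/70)(40/70)D² / 12.3² = 0.245 D² / 151.29. For D = 0, 5, 10, 12 this is 0, 0.04, 0.16, 0.23. The residual SD after adjustment is 12.3 × √(1 − R²).

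**4. Simulated power and type I error.** 100,000 trials per scenario, normal outcomes, 15+15 and 20+20 by arm, sham total SD held at 12.3. *Proportional* means that each procedure's active mean is 0.67 of its sham mean; *constant* means a shift of 7.887 in both. Power entries are unadjusted / adjusted.

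| Gap | Power, proportional | Power, constant | Alpha of t-test | Mean 95% CI width, proportional |
|---|---|---|---|---|
| 0 | 75.6 / 75.6% | 75.1 / 75.1% | 5.0% | 11.69 / 11.69 |
| 5 | 76.1 / 77.0% | 75.7 / 77.0% | 4.5% | 11.63 / 11.46 |
| 10 | 78.5 / 82.1% | 76.9 / 82.2% | 3.2% | 11.45 / 10.74 |
| 12 | 80.2 / 85.3% | 77.9 / 85.6% | 2.5% | 11.34 / 10.29 |

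The adjusted test's alpha was 4.9 to 5.0% throughout. The two gap-0 rows describe the same situation (exact value 75.3%), so they also show the simulation error. In participants, the CI gain is 70 × [(unadjusted width / adjusted width)² − 1]: about 0, 2, 10 and 15.

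**5. What would restore 80% power.** An R² of about 0.08 (normal approximation) to 0.11 (t). By step 3 reversed, D = 12.3 × √(R²/0.245), a gap of roughly 7 to 8 points.

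**6. Sensitivity.**
- *12.3 is the within-procedure SD.* The gains are almost the same, but at a gap of 12 unadjusted power falls to 69.8% (proportional) or 67.9% (constant), while adjusted power stays near 75%.
- *80 participants (34+46 assumed), proportional:* 81.0/81.0, 81.6/82.4, 84.1/87.0 and 85.6/89.7%.
- *Hip and knee as separate strata (30+20+20, equal means), proportional:* 75.3/75.2, 76.1/77.0, 78.6/82.1 and 80.2/85.4%.
- *Rank tests (40,000 trials, proportional), Mann-Whitney / van Elteren:* 72.7/72.2, 73.7/73.8, 76.0/79.5 and 77.8/82.7%.

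**7. Amputees.** The large-sample variance of ANCOVA relative to the change score is (1 − r²)/(1 + k² − 2rk), with r the Day 0 to Day 28 correlation and k = SD Day 0 / SD Day 28. For assumed r = 0.3, 0.5, 0.7: 0.65, 0.75, 0.85 at k = 1; 0.78, 0.89, 0.98 at k = 0.8; 0.85, 0.95, 1.00 at k = 0.7. Simulated with an assumed 40 amputees (60,000 trials), the ranges are 0.66 to 0.88, 0.81 to 1.01 and 0.88 to 1.03.

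**The case against.** The strongest case is that this is a small matter in a self-described exploratory pilot. The unadjusted test errs in the safe direction, the gain starts at zero, and the larger gains need gaps of 10 to 12 points on a mean of 23.9. A gap of 12 means procedure means of about 17 and 29, which nothing in the protocol supports. This stands as a limit on size: the benefit is unknown and may be negligible. It does not argue for leaving the strata out, since the linear model loses nothing measurable when the gap is zero.

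The plan also ties no test explicitly to the summed score; the wording on tests is general, and the protocol disclaims an analysis plan. That is fair as to wording. But the same section then sets a Phase II primary outcome, a power calculation, tests and a P<0.05 threshold, and no analysis by procedure is named for any of them.

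The improvement is not quite free on the rank-test route: van Elteren loses about 0.5 power points at a gap of 0 and roughly breaks even at 5. This stands, and favours the linear model as the main analysis.

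For amputees, no test is named, so baseline adjustment is not excluded, and in a group of about 40 ANCOVA can be very slightly less precise. This too stands, which is why that point is secondary.

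**Conclusion.** The concern holds as an efficiency improvement that should be made; it is not a validity error. Phase II randomises within procedure, yet no analysis using procedure is specified. The consequence is a conservative test: true alpha of 2.5 to 4.5% at assumed gaps of 12 to 5 points, against a nominal 5%. In the linear model the power gained by adjustment is nil at no gap, about 1 point at a gap of 5, and at most about 8 points at a gap of 12.

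These figures rest on assumed gaps, normal outcomes, no dropout, and 12.3 read as the SD across both procedures. The direction does not depend on the gaps; the size does. Because 70 participants give only about 75% unadjusted power on the plan's inputs, even a moderate procedure difference would make the adjustment worthwhile. The amputee gain ranges from about a third of the variance to none.

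**What to change.** In the statistical paragraphs of section 9, specify for the Phase II primary outcome:

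1. A linear model for the summed pain score with terms for arm and for the procedure strata used in the randomisation list, reporting the adjusted difference with its 95% CI and P value.
2. If a rank test is needed, a van Elteren test stratified by procedure in place of Mann-Whitney.
3. Whether hip and knee arthroplasty form one stratum or two. Section 10 lists "knee or hip arthroplasty" as a single item, and section 9 does not say.

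The Phase II total (70 or 80) should be reconciled at the same time.

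Secondary, for amputees: analyse Day 28 average pain of the initial period by ANCOVA with Day 0 pain as covariate, separately for residual and phantom limb pain.

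Cost: a few sentences, with no new data or participants. The linear model uses one degree of freedom, or two if hip and knee are separate; the two-degree version changed simulated power by 0.1 point or less when procedures did not differ.

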10. HUMAN PARTICIPANTS

We will recruit a convenience sample with a maximum of **270 participants in total (all participants who sign an informed consent included)**. Selection for inclusion will not be based on race, ethnicity, sexual identity, or socioeconomic status. There will be no participants from vulnerable populations, such as pregnant women, children, or prisoners.

Inclusion criteria (amputees): Adult patients of at least 18 years of age [19 years in Alabama and Nebraska], (1) with an upper or lower limb amputation at least 12 weeks prior to enrollment distal to the shoulder or hip (femoral head remaining), respectively, and including at least one metacarpal or metatarsal bone, respectively; (2) who experience at least moderate residual and/or phantom limb pain—defined as a 3 or higher on the Numeric Rating Scale (NRS; 0-10, 0= no pain; 10=worst imaginable pain)—at least daily for the previous 2 months; and (3) willing to avoid both changes to their analgesic regimen as well as elective surgical procedures for 70 days after initiation of treatment with PEMF therapy.

Inclusion criteria (surgical patients): Adult patients of at least 18 years of age undergoing one of the surgical procedures listed below:

- a. non-mastectomy breast surgery with a single-injection paravertebral nerve block
- b. laparoscopic or open cholecystectomy
- c. laparoscopic sleeve gastrectomy
- d. percutaneous nephrolithotomy
- e. ventral hernia repair
- f. inguinal hernia repair
- g. knee or hip arthroplasty
- h. foot/ankle surgery with at least moderate pain anticipated
- i. shoulder acromioclavicular joint repair, labral repair, subacromial decompression, or Bankart repair (without rotator cuff repair)
- j. hand/forearm/elbow/shoulder surgery with at least moderate pain anticipated
- k. spinal surgery with at least moderate pain anticipated

Exclusion criteria: (1) concurrent use of an implanted pulse generator (e.g., cardiac pacemaker); (2) pregnancy; (3) incarceration. **Surgical participants only:** (4) chronic opioid/tramadol use (daily use within the 2 weeks prior to surgery and duration of use > 4 weeks); (5) neuro-muscular deficit of the surgical area/limb; (6) a planned postoperative perineural local anesthetic infusion.

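### Phase II is sized at 70 in one place and at 80 in two others, and on the protocol's own inputs 70 falls short of the stated 80% power while 80 just reaches it

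*Combined protocol and SAP*

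**What the plan says.** The sample size text in Section 9 opens with "For Phase II, there will be a total of 70 surgical participants" and closes with "we will enroll a total of 70 participants in Phase II: cholecystectomy (n=30), and hip and knee arthroplasty (n=40". These agree with each other, since 30 + 40 = 70.

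Two other places give 80. Section 7 (Background and Significance) lists the devices, "as well as SofPulse for the subsequent 80 surgical subjects of Phase II". The treatment assignment paragraph of Section 9 begins its Phase II sentence with "For the subsequent 80" and goes on to say which device each arm receives.

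The planning values in Section 9 are as follows. For the control arm, "we anticipate the sham group to have an anticipated mean (SD) of 23.9 (12.3". The smallest difference of interest is a 33% reduction. The error rates are given by "Assuming a two-sided type I error protection of 0.05 and a power of 0.80". From these the plan derives about 25 patients per group, using an online calculator, and raises the total to 70 to cover more variability than expected. It gives no dropout rate. The listed test for normally distributed continuous data is Student's t-test, and allocation is 1:1.

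Section 10 caps the whole study at "270 participants in total (all participants who sign an informed consent included". It then gives one surgical eligibility list, items a to k, introduced by "Inclusion criteria (surgical patients): Adult patients of at least 18 years of age undergoing one of the surgical procedures listed below". The list does not mention Phase I or Phase II.

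**The concern.** Both figures stand in current text and both describe Phase II enrolment. If the 80 is followed, the quotas place only 70, so 80 - 70 = 10 participants (10/80 = 12.5%) have no assigned procedure. If the 70 is followed, the assignment text describes ten people who will not exist.

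Phase II is the only part of the study with a sample size calculation, and Section 9 says it is analysed separately from the rest. Its primary outcome is judged at P<0.05. For such a comparison, the point at which enrolment ends should be fixed in advance. Two published totals leave that open, and they also leave open what power the comparison was designed to have.

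**Working it through.** **Does anything bridge 70 and 80?** No dropout, screen-failure or replacement allowance is stated for Phase II. The overall cap does not settle the matter either. With 150 surgical participants in Phase I, 270 - 150 - 70 = 50 and 270 - 150 - 80 = 40. Both leave room for amputees, no amputee target is given, and 270 is a maximum that counts everyone who signs consent.

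**Inputs (all from the Section 9 sample size text).** Sham mean 23.9; SD 12.3; reduction 33%; two-sided alpha 0.05; power 0.80. Equal allocation comes from the treatment assignment paragraph.

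- Difference: 0.33 × 23.9 = 7.887
- Standardised difference: 7.887 / 12.3 = 0.641

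**Reproducing the plan's 25 per group.** The normal approximation is n per group = 2 × [(1.960 + 0.842) × SD / difference]².

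- 2 × (2.802 × 12.3 / 7.887)² = 38.2, so 39 per group (78 in total)
- The two-sample t-test gives 39.2, so 40 per group (80 in total)

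The stated 25 does not reproduce. Other readings were tried:

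| Variant | n per group |
|---|---|
| Reduction of exactly one third (normal approximation) | 38 |
| One-sided 0.05 | 31 |
| Active-arm SD shrunk to 0.67 × 12.3 = 8.24 | 28 |
| One-sample test against a fixed mean | 20 |
| Reduction of 40% instead of 33% | 26 |

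Only the 40% reduction comes close, and it is not the stated effect. Keeping the 33% effect, 25 per group would need an SD of about 9.95.

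**Power at each stated total.** Under the normal approximation, power = Φ(0.641 × √(n/2) - 1.960), with n per group.

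| Total | n per group | Power, normal | Power, t-test |
|---|---|---|---|
| 50 (the plan's calculation) | 25 | 62.1% | 60.3% |
| 70 | 35 | 76.5% | 75.3% |
| 80 | 40 | 81.8% | 80.8% |

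**Is there a margin for higher variability?** The largest SD that keeps 80% power is 7.887 × √(n/2) / 2.802 (normal approximation).

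- At 35 per group: 11.8, below the anticipated 12.3
- At 40 per group: 12.6, barely above it

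So the increase from 50 to 70 gives no protection against a larger SD. At 70 the design is short of its target even if the SD is exactly as anticipated.

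**The case against.** The document calls the study an exploratory pilot, so a difference of ten participants may seem unimportant. That has some weight for Phase I and the amputees. It has less for Phase II, which has its own hypothesis, alpha, power and required number.

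A second objection is that the SD is given only for the sham arm. If the active-arm SD fell in proportion to its mean, 28 per group (56 in total) would suffice and 70 would be enough. The arithmetic is right, but the documents do not state that assumption, and it still does not yield 25.

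A reader might also infer that Phase II has two conflicting populations, because nine of the eleven listed procedure categories lie outside the Phase II quotas. The documents do not support that. The Section 10 list covers the whole study and is silent on phase; it does not say that every category is open in Phase II. Section 9 states a narrower Phase II enrolment plan, and a narrower plan inside a wider list is not a contradiction. Enrolling a hernia patient in Phase II would satisfy Section 10 but depart from Section 9. Randomization is also stratified by procedure at a single center, so a stray procedure would mainly affect variance and generalisability rather than bias the comparison. Nor does the text say outright that 23.9 (12.3) comes only from the two named procedure groups. It attributes the values to Phase I sham patients, and the sentence on the named procedures only suggests the restriction.

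Finally, it is tempting to treat 80 as a slip and change it to 70. Nothing in the documents shows which figure is the slip, and 70 is the one that misses the stated power.

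**Conclusion.** The concern holds for the size of Phase II. Section 9's sample size text says 70, Section 7 and the Section 9 treatment assignment text say 80, and nothing reconciles them. The supporting figure of about 25 per group is also wrong on the stated inputs; about 40 per group are needed. Power is about 75% at 70 and about 81% at 80, so the choice of total decides whether the plan meets its own 80% target.

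These figures assume a common SD of 12.3, a difference of 7.887, equal groups, no missing outcomes and an unadjusted two-sample t-test. Losses would lower both powers, and 80 has almost no room for them.

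The silence of the eligibility list on phase is a drafting gap that merits a clarification, not a second contradiction.

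**What to change.** 1. Redo the Section 9 calculation and show the difference, the SD assumed in each arm, the test and the resulting number per group. If a smaller active-arm SD or a larger effect was intended, say so and justify it.
2. Choose one Phase II total. State it in Section 7 and in both the treatment assignment and the sample size text of Section 9, with cholecystectomy and arthroplasty quotas that add up to it.
3. Report the power that total delivers on the stated inputs: about 75% if 70 is kept, about 81% if 80 is chosen. If 70 is kept, drop the statement that it allows for extra variability.
4. State that Phase II enrolment closes when the quotas are full.
5. As a clarification only, note in Section 10 that Phase II enrols from items b and g, as Section 9 already plans.

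Keeping 70 costs only a wording amendment and an open statement of the lower power. Choosing 80 means ten more participants than the present quotas provide, within the 270 cap provided that consents elsewhere in the study leave room. Neither choice adds procedures or data items.
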